## 4.2 Exclusion Criteria

Subjects meeting any of the following criteria must not be enrolled in the study:

- 1) Any other malignancy from which the patient has been disease-free for less than 3 years, with the exception of adequately treated and cured basal or squamous cell skin cancer, superficial bladder cancer or carcinoma *in situ* of the cervix.
- 2) Autoimmune disease: Patients with a history of inflammatory bowel disease, including ulcerative colitis and Crohn's Disease, are excluded from this study, as are patients with a history of symptomatic disease (eg, rheumatoid arthritis, systemic progressive sclerosis [scleroderma], systemic lupus erythematosus, autoimmune vasculitis [eg, Wegener's Granulomatosis]); motor neuropathy considered of autoimmune origin (e.g. Guillain-Barre Syndrome and Myasthenia Gravis).
- 3) Any underlying medical or psychiatric condition, which in the opinion of the

investigator will make the administration of ipilimumab hazardous or obscure the interpretation of AEs, such as a condition associated with frequent diarrhea.

- 4) Any non-oncology vaccine therapy used for prevention of infectious diseases (for up to 1 month before or after any dose of ipilimumab).
- 5) Concomitant therapy with any of the following: IL-2, interferon, other non-study immunotherapy regimens, cytotoxic chemotherapy, other investigation therapies
- 6) Concomitant therapy with immune-suppressants or chronic use of systemic corticosteroids.
- 7) Must be off prior systemic therapies for 2 weeks prior to enrollment. Patients that have been previously treated with systemic therapy adjuvantly or for metastatic disease remain eligible as long as they continue to meet all other eligibility criteria (oligometastatic, no visceral metastasis > 5 cm, eligible for SABR)
- 8) Prior radiation therapy that at the treating physician's discretion makes SABR unsafe
- 9) No clinically significant evidence of pleural effusion or ascites
- 10) Congestive heart failure > class II NYHA or unstable angina
- 11) Cardiac ventricular arrhythmias requiring anti-arrhythmic therapy
- 12) Major surgery, open biopsy or significant traumatic injury within 2 weeks of first dose of study drug
- 13) A visceral metastasis greater than 8 cm
- 14) A visceral metastasis that due to its location cannot be safely treated with SABR
- 15) Women of childbearing potential (WOCBP), defined above in Section 4.1, who:
  - a. are unwilling or unable to use an acceptable method of contraception to avoid pregnancy for their entire study period and for at least 3 months after cessation of study drug, or
  - b. have a positive pregnancy test at baseline, or
  - c. are pregnant or breastfeeding.
- 16) Male subjects of reproductive potential who are unwilling or unable to use an acceptable method of contraception with their female partners for their entire study

period and for at least 3 months after cessation of study drug.

- 17) Prisoners or subjects who are compulsorily detained (involuntarily incarcerated) for treatment of either a psychiatric or physical (eg, infectious) illness.
- 18) Have a known immediate or delayed hypersensitivity reaction or idiosyncrasy to drugs chemically related to study drug, or excipients or to dimethyl sulfoxide (DMSO)

Sexually active WOCBP must use an effective method of birth control during the course of the study, in a manner such that risk of failure is minimized. Before study enrollment, WOCBP must be advised of the importance of avoiding pregnancy during study participation and the potential risk factors for an unintentional pregnancy. All WOCBP MUST have a negative pregnancy test before first receiving ipilimumab. If the pregnancy test is positive, the patient must not receive ipilimumab and must not be enrolled in the study.

#### **4.3 Gender/Minority/Pediatric Inclusion for Research**

This study includes both genders and minority patients. Pediatric patients are excluded.

#### **4.4 Subject Recruitment and Screening**

Patients who are 18 year of age or older with oligometastatic melanoma are eligible for this study. Patients can be recruited from PI or co-investigators' clinical practices. Potential study subject should be notified to PI and study designated research nurse/research associate. Appropriate laboratory or diagnostic testing necessary to meet any noted inclusion or exclusion criteria will be ordered through the recruiting physician. PI of the study will screen and determine the final eligibility of the subject for enrollment.

#### **4.5 Early Withdrawal of Subjects**

##### **4.5.1 When and How to Withdraw Subjects**

Patients will be informed that they have the right to withdraw from the study at any time for any reason, without prejudice to their medical care. The investigator also has the right to withdraw patients from the study for any of the following reasons:

1. Intercurrent illness
2. Occurrence of an unacceptable adverse event
3. Patient request
4. Protocol violations
5. Non-compliance
6. Administrative reasons
7. Failure to return for follow-up

8. General or specific changes in the patient's condition unacceptable for further treatment in the judgment of the investigator

At the time of withdrawal, all study procedures outlined for the End of Study visit should be completed. The primary reason for a patient's withdrawal from the study is to be recorded in the source documents.

#### 4.5.2 Data Collection and Follow-up for Withdrawn Subjects

According to FDA regulations, when a subject withdraws from the study, the data collected on the subject to the point of withdrawal remains part of the study database and may not be removed.

A subject who is withdrawing needs to state whether he/she wishes to provide continued follow-up and further data collection subsequent to withdrawal from the interventional portion of the study.

If a subject withdraws from the interventional portion of the study, but agrees to continued follow-up of associated clinical outcome information as described in the previous bullet, the subject will continue follow up visit and evaluation per the protocol.

If a subject withdraws from the interventional portion of a study and does not consent to continued follow-up of associated clinical outcome information, study data related to the subject collected prior to the subject's withdrawal from the study will be included in the study analysis.

## 5.0 STUDY DRUG

### Ipilimumab

#### 5.1 Dose Calculations

Each patient will receive ipilimumab 3 mg/kg infusions over 90 minutes (not bolus or IV push) on weeks 1, 4, 7, & 10.

Calculate **Total Dose** as follows:

Patient body weight in kg x (3) mg = total dose in mg

Calculate **Total Infusion Volume** as follows:

Total dose in mg ÷ 5 mg/mL = infusion volume in mL

Calculate **Rate of Infusion** as follows:

Infusion volume in mL ÷ 90 minutes = rate of infusion in mL/min.

For example, a patient weighing 114 kg (250 lb) would be administered 342 mg of ipilimumab (114 kg x 3 mg/kg = 342 mg) with an infusion volume of 342 mL (342 mg ÷ 1 mg/mL = 342 mL) at a rate of approximately 2.5 mL/min (342 mL ÷ 2.5 mL/min) in 137 minutes.

The total dose must be calculated using the most recent subject weight (obtained within 3 days of the dosing visit, and prior to the infusion). The maximum dose of ipilimumab is 400 mg. Therefore, patients  $\geq$  133 kg should not receive a dose > 400 mg.

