#### 3.1.2 Treatment

- The recommended dose of ipilimumab as a single agent is 3 mg/kg administered intravenously over a 90-minute period every 3 weeks for a total of four doses, as tolerated.
- Laboratory evaluations should be performed and the results examined before administration of each ipilimumab dose.
- As durable disease stabilization and/or objective tumor response can be seen after early progression before Week 12, it is recommended that, in the absence of dose-limiting toxicities (eg, serious immune-mediated adverse reactions), all four doses of ipilimumab be administered over the initial 12 weeks even in the setting of apparent clinical progression, providing the subject's performance status remains stable.
- All subjects who are treated with ipilimumab including those who may have discontinued treatment for drug-related AEs and/or who have evidence of clinical progression during the treatment period, should obtain a 12-week tumor assessment.
- Based on clinical experience in the ongoing and completed melanoma studies, the following recommendations apply for subject management in light of the Week 12 or later tumor assessments:

The appearance of new lesions in subjects with other stable or shrinking baseline tumor burden may be experiencing clinical benefit and should continue in follow-up and/or maintenance therapy before alternative anti-cancer agents are considered. These subjects can be seen to have continued tumor shrinkage in follow-up scans.

As long as overall tumor burden is stable or decreasing, subjects should remain in follow-up and/or maintenance, even in the presence of new lesions.

Clinical progression warranting alternative anti-cancer treatment should be considered only in subjects whose overall tumor burden appears to be substantially increased and/or in subjects whose performance status is decreased.

In our study we propose to evaluate a combination of ipilimumab and SABR in patients with oligometastatic melanoma in a phase II trial.

The study will consist of the following schedule: ipilimumab will be administered on week 1 at a dose of 3 mg/kg.

Subsequent cycles of ipilimumab will be given every three weeks (week 4, 7, & 10).

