#### *Preparation of Solution*

Allow the vials to stand at room temperature for approximately 5 minutes prior to preparation of infusion.

Withdraw the required volume of ipilimumab and transfer into an intravenous bag.

Dilute with 0.9% Sodium Chloride Injection, USP or 5% Dextrose Injection, USP to prepare a diluted solution with a final concentration ranging from 1 mg/mL to 2 mg/mL. Mix diluted solution by gentle inversion.

Store the diluted solution for no more than 24 hours under refrigeration (2°C to 8°C, 36°F to 46°F) or at room temperature (20°C to 25°C, 68°F to 77°F).

Discard partially used vials or empty vials of ipilimumab.

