#### *Administration Instructions*

Do not mix ipilimumab with, or administer as an infusion with, other medicinal products.

Flush the intravenous line with 0.9% Sodium Chloride Injection, USP or 5% Dextrose Injection, USP after each dose.

Administer diluted solution over 90 minutes through an intravenous line containing a sterile, non-pyrogenic, low-protein-binding in-line filter.

See the current Investigator Brochure for additional information on allowable filter types. The infusion must be completed in 90 minutes with a 10 ml normal saline flush at the end.

Ipilimumab should be administered under the supervision of a physician experienced in the use of intravenous (IV) agents. Ipilimumab is administered as an IV infusion only.

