### 6.3.4 Dose Considerations

Lung SABR recommended doses: 18 Gy x 3 to peripheral lung masses, 10 Gy x 5 to central lung masses given 2 fractions per week

Liver SABR recommended doses: 10 Gy x 5 given 2-3 fractions per week

Nodal station SABR recommended doses: 6 Gy x 6 given 3 fractions per week

Adrenal SABR recommended doses: 12 Gy x 3,

Vertebral body SABR recommended doses: 16-18 Gy x 1 respecting normal tissue spinal cord constraints particularly no more than 10 Gy to 10% of cord volume

Brain parenchymal SABR recommended doses: 24 Gy x 1, 18 Gy x 1, 15 Gy x 1 to < 2.0 cm, 2.0-3.0 cm, and >3 cm brain metastases, respectively dosed to the 50-70% isodose line if using Gamma Knife SRS.

Fractionation: Treatment shall be given 2-3 days per week at the treating radiation oncologist's discretion.

Dose Homogeneity: The dose throughout the treatment volume will be within 10% of the prescribed dose. Wedges, compensation, and other methods of generating a uniform dose distribution are encouraged. IMRT can be used to shape dose around critical normal structures.

Isodose Plans: The isodose distribution for the composite plan shall be calculated. The prescription point and the outline of the tumor volume shall be shown.

Image guidance: Pre-treatment kilovoltage on board CT imaging will be done for localization, and shifts will be made as appropriate per the treating radiation oncologist.

Treatment Modification: Uninterrupted treatment is planned, and SABR fractions should occur during the period between the 2nd and 3rd doses of ipilimumab (generally weeks 5-6). SABR can be delayed at the physician's discretion if there is concern for overlapping toxicities with ipilimumab, but SABR should always be delivered between infusion 2 and infusion 3 of ipilimumab. The entire course of SABR should be delivered within the 3 week period between ipilimumab infusions, except in the case of a grade 3+ toxicity in the middle of the course of SABR. If a grade 3+ toxicity occurs during SABR which interrupts the delivery of SABR, then the final SABR fractions will be delivered after the toxicity returns to grade or lower with appropriate supportive care measures.

On Treatment Management: The patient will be examined at least once a week during the course of radiation therapy.

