### **9.1 Identification**

Ipilimumab is available in concentrations of 5 mg/mL (50 mg/10 mL and 200 mg/40 mL). The sterile solution in the vial is clear and colorless. Ipilimumab is administered via intravenous infusion only.

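### The infusion formula and 137-minute example in 5.1, the 10% homogeneity sentence in 6.3.4 and the nodal SABR schedule in 3.1.2 each contradict other protocol text

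*Combined protocol and SAP*

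**What the plan says.** **Infusion.** Section 5.1 sets a 90-minute infusion and defines the volume as "Total dose in mg ÷ 5 mg/mL = infusion volume in mL". It then obtains the rate by dividing that volume by 90 minutes. Its example for a 114 kg patient takes 342 mg, switches to 1 mg/mL to reach 342 mL, and infuses "at a rate of approximately 2.5 mL/min (342 mL ÷ 2.5 mL/min) in 137 minutes". Section 5.2 tells the pharmacy "to prepare a diluted solution with a final concentration ranging from 1 mg/mL to 2 mg/mL", and its administration paragraph says "The infusion must be completed in 90 minutes with a 10 ml normal saline flush at the end". Section 3.1.2 gives the recommended regimen as "administered intravenously over a 90-minute period every 3 weeks for a total of four doses". Section 9.1 shows where the 5 comes from: "Ipilimumab is available in concentrations of 5 mg/mL".

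**Homogeneity.** Section 6.3.4 states: "The dose throughout the treatment volume will be within 10% of the prescribed dose". The same section has brain lesions "dosed to the 50-70% isodose line if using Gamma Knife SRS". Section 6.3.5 delivers the prescription dose at the PTV margin, typically on a line between 60% and 90%. It states that a central hotspot will exist, equal to the prescribed dose times the reciprocal of that line.

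**SABR schedules.** Section 3.1.2 lists nodal stations at 6 Gy x 5. The Study Summary, 6.1 and 6.3.4 list 6 Gy x 6. Sections 3.1.2 and 6.3.4 separate peripheral lung (18 Gy x 3) from central lung (10 Gy x 5), while the Study Summary and 6.1 give only 18 Gy x 3 for lung.

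**The concern.** These are instructions that pharmacy, nursing and radiation planning staff carry out, and following one as written breaks another. The 5.1 formula describes undiluted drug, and the 5.1 example overruns the infusion time. The infusion rate also matters beyond the first bag. The guidance in 5.5 for infusion reactions and drug fever is expressed relative to the initial, planned or previous rate, so an ambiguous starting rate carries through to those steps. A radiation plan that complies with 6.3.5 is, read literally, a deviation from 6.3.4. A nodal patient who has had five fractions has finished treatment under 3.1.2 but is one fraction short under 6.3.4. At stake are treatment consistency and patient safety.

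**Working it through.** **1. Infusion (5.1, 5.2, 9.1)**

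Inputs: 3 mg/kg; 114 kg; 90 minutes; formula divisor 5 mg/mL; permitted final concentration 1–2 mg/mL; example rate 2.5 mL/min; maximum dose 400 mg.

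- Dose: 114 x 3 = 342 mg, as stated.
- The example as printed: 342 ÷ 1 = 342 mL, and 342 ÷ 2.5 = 136.8 min, which rounds to the stated 137. The example agrees with itself.
- The 5.1 formulas as printed: 342 ÷ 5 = 68.4 mL, and 68.4 ÷ 90 = 0.76 mL/min. The volume is one fifth of the example's, and its concentration is 5 mg/mL, outside 1–2 mg/mL. The section's formulas therefore give neither the example's volume nor its rate.
- Duration of the example against the rule: 136.8 ÷ 90 = 1.52, or 52% too long.
- Permitted dilution over 90 minutes: 342 ÷ 90 = 3.8 mL/min at 1 mg/mL; 342 ÷ 2 = 171 mL and 171 ÷ 90 = 1.9 mL/min at 2 mg/mL.
- If the example's 2.5 mL/min at 1 mg/mL were used for other patients, 90 minutes would be exceeded above 2.5 x 90 ÷ 3 = 75 kg, and the 400 mg maximum would take 400 ÷ 2.5 = 160 min.
- If the bag were diluted as in 5.2 but the pump set by the 5.1 formulas, the rate would be dose ÷ (5 x 90) = dose ÷ 450. The infusion would then last 450 min at 1 mg/mL or 225 min at 2 mg/mL, whatever the weight.

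**2. Homogeneity (6.3.4, 6.3.5)**

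Hotspot as a fraction of prescription = 1 ÷ isodose line. The ceiling under the 10% sentence is 110%.

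| Line | Hotspot | Applies to |
|---|---|---|
| 90% | 1 ÷ 0.90 = 111% | 6.3.5, upper end |
| 80% | 1 ÷ 0.80 = 125% | 6.3.5, typical |
| 60% | 1 ÷ 0.60 = 167% | 6.3.5, lower end |
| 70% | 1 ÷ 0.70 = 143% | Gamma Knife, upper end |
| 50% | 1 ÷ 0.50 = 200% | Gamma Knife, lower end |

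Staying within 110% needs a line of at least 1 ÷ 1.10 = 90.9%. No line in either stated range reaches that.

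**3. Nodal schedule**

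6 x 5 = 30 Gy against 6 x 6 = 36 Gy. The difference is 6 ÷ 30 = 20% of the lower dose.

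**The case against.** On the infusion, 5.2 is clear about both dilution and duration, so a pharmacy that follows it would not send out 5 mg/mL. Dose ÷ 5 mg/mL is the volume to withdraw from the vial, so the formula is probably mislabelled rather than misconceived. The example errs towards a slower infusion. The protocol itself allows slower rates after reactions or recurrent drug fever, and nothing in it suggests that 137 minutes is harmful. The 2.5 mL/min figure belongs to one example and is not a rule for all patients. In 3.1.2 the 90 minutes is part of a recommendation; the binding wording is in 5.1 and 5.2.

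On homogeneity, 6.3.5 says the lines are typically 60–90%, the breach at the 90% line is only 1.1 percentage points, and the detailed dosimetry text makes the intended technique plain. On the nodal dose, the schedules are labelled suggested or recommended. A three-to-one count does not settle intent either, because 1.2.3 describes SABR as one to five treatments.

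Much of this stands as a limit on weight. It lowers the chance of harm and explains how the errors probably arose. It does not reconcile the text. Section 5.1 still prints a wrong volume and a rate that cannot be combined with 5.2. The word typically does not help the 10% sentence, because 6.3.5 sets its lines in explicit contrast to 95–100%, and Gamma Knife is far outside the limit at every stated line. The nodal point is the weakest of the three, and its correction needs clinical confirmation.

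**Conclusion.** The point holds and should be fixed. Section 5.1 contains a volume formula off by a factor of five from its own example (2.5 to 5 times too small for the permitted dilutions: 171 ÷ 68.4 and 342 ÷ 68.4), and an example 52% longer than the required infusion time. The 10% sentence cannot be met at any stated isodose line. The nodal schedule differs by 6 Gy between sections. The homogeneity result assumes that the treatment volume in 6.3.4 is the PTV in which 6.3.5 places the hotspot. The figures for patients above 75 kg and for the 400 mg dose apply only if the example's rate and concentration are reused. The milligram dose is the same under every reading, and neither the sample size nor the 8-of-32 decision rule depends on any of this.

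**What to change.** 1. **Section 5.1:** define infusion volume as total dose divided by the final diluted concentration (1–2 mg/mL). If the 5 mg/mL line is wanted, keep it separately and label it as the volume to withdraw from the vial. Restate the 114 kg example as 342 mL at 3.8 mL/min (1 mg/mL) or 171 mL at 1.9 mL/min (2 mg/mL), each over 90 minutes. The 342 mg stays.
2. **Section 6.3.4:** delete the 10% sentence, or replace it with a limit compatible with 60–90% lines and with 50–70% for Gamma Knife.
3. **Section 3.1.2:** change nodal SABR to 6 Gy x 6, matching the dedicated dose section, unless the radiation lead confirms 6 Gy x 5; in that case change the other three places. If six fractions stay, widen the description in 1.2.3 to allow for them.
4. **Minor:** carry the peripheral and central lung schedules into the Study Summary and 6.1. At the same time align their bone entry (18 Gy x 1) with the vertebral entry in 3.1.2 and 6.3.4 (16–18 Gy x 1).

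The cost is a text-only amendment, with no extra patients, visits or analyses.

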#### 5.2 Storage, Preparation, and Administration

Ipilimumab injection must not be administered as an IV push or bolus injection. Care must be taken to assure sterility of the prepared solutions, since the drug product does not contain any antimicrobial preservatives or bacteriostatic agents.

Do not shake product.

Inspect parenteral drug products visually for particulate matter and discoloration prior to administration. Discard vial if solution is cloudy, there is pronounced

discoloration (solution may have pale yellow color), or there is foreign particulate matter other than translucent-to-white, amorphous particles.

#### *Preparation of Solution*

Allow the vials to stand at room temperature for approximately 5 minutes prior to preparation of infusion.

Withdraw the required volume of ipilimumab and transfer into an intravenous bag.

Dilute with 0.9% Sodium Chloride Injection, USP or 5% Dextrose Injection, USP to prepare a diluted solution with a final concentration ranging from 1 mg/mL to 2 mg/mL. Mix diluted solution by gentle inversion.

Store the diluted solution for no more than 24 hours under refrigeration (2°C to 8°C, 36°F to 46°F) or at room temperature (20°C to 25°C, 68°F to 77°F).

Discard partially used vials or empty vials of ipilimumab.

#### *Administration Instructions*

Do not mix ipilimumab with, or administer as an infusion with, other medicinal products.

Flush the intravenous line with 0.9% Sodium Chloride Injection, USP or 5% Dextrose Injection, USP after each dose.

Administer diluted solution over 90 minutes through an intravenous line containing a sterile, non-pyrogenic, low-protein-binding in-line filter.

See the current Investigator Brochure for additional information on allowable filter types. The infusion must be completed in 90 minutes with a 10 ml normal saline flush at the end.

Ipilimumab should be administered under the supervision of a physician experienced in the use of intravenous (IV) agents. Ipilimumab is administered as an IV infusion only.

### **5.3 Dose Modification**

#### ***Ipilimumab Dose Skipping Rule***

Decisions to skip an ipilimumab dose must be made on specified safety criteria. Treatment with ipilimumab will be skipped or discontinued if the subject experiences at least one adverse event, specified below, considered by the investigator to be “**possibly,**” “**probably,**” or “**certainly**” related to ipilimumab

**treatment.** The investigator should contact BMS for any adverse event that will prompt a skipped dose or discontinuation of ipilimumab.

The following criteria will be used to determine dose skipping, restarting doses, or discontinuing ipilimumab.

